6.2.11 Microarray Studies

Blood for PBMCs for microarray studies will be collected at entry and weeks 4 and 24. Specimens will need immediate on-site processing and storage. All

specimens must be **shipped overnight, frozen to the central laboratory (UCSD)** on week 36.

Blood volume: 30 mL

6.3.12 PBMCs for storage

Blood for PBMCs will be collected and **shipped ambient, overnight and in real-time to the central laboratory (UCSD)** at pre-entry, entry and weeks 4 and 24.

Blood volume: 10 mL

6.3.13 Lumbar Puncture

For subjects enrolled in the CSF Sub-Study: CSF will be collected at baseline, weeks 4 and 24 for cell counts, protein, glucose, HIV RNA and markers of immune activation.

Cerebral Spinal Fluid volume: 25 mL

6.3.14 Plasma MVC plasma concentration

For subjects enrolled in the CSF Sub-Study: Blood for plasma MVC concentrations will be collected at baseline and weeks 4 and 24.

Blood volume: 20 mL

6.3.15 Adherence Assessment

Adherence assessment will be performed by the study coordinator using standard ACTG adherence format on weeks 2, 4, 8, 12, 24, and 36 of therapy and in instances of virologic failure and/or premature treatment discontinuation.

6.4 Off-Drug Requirements

Additional safety monitoring and reporting of serious adverse experiences (SAEs) continues to be required upon completion or discontinuation of study treatment regardless of whether a protocol follow-up period is scheduled to occur. Adverse experiences occurring during the immediate 8-week period after the last dose of study treatment which meet SAE reporting requirements must be reported to the **CCTG Data Center**. Additionally, after 8 weeks OFF study treatment, there are four types of events that must be reported to the **CCTG Data Center** if the relationship to the study drug is assessed by the site physician as definitely, possibly, or unable to judge: DEATHS, NEW ONSET CANCERS, CONGENITAL ANOMALIES, AND PERMANENT DISABILITIES.

7 TOXICITY MANAGEMENT

Specific management of toxicity will be discussed only for the study-provided medication, MVC. The management of medication related toxicities should be undertaken by the local investigators, with guidance available from the protocol team, protocol pharmacist and pharmaceutical sponsor, to insure the optimal safety and efficacy for the individual subject.

7.1 Commonly occurring adverse events

7.1.1 Grade 1 or 2

Subjects who develop a Grade 1 or 2 adverse event or toxicity may continue MVC without alteration of the dosage. Those subjects experiencing Grades 1 or 2 adverse events which results in discontinuation of the MVC should be removed from the study.

7.1.2 Grade 3

Management of Grade 3 toxicities should be discussed with the protocol team via email. Please refer to the subsequent sections for management of specific events.

In the event that a subject develops a **symptomatic** Grade 3 reaction considered to be **MVC-related**, the study drug should be discontinued and the subject should be followed weekly until resolution of the adverse event. Once Grade 3 is resolved the subject should be removed from study.

7.2.3 Grade 4

Management of Grade 4 toxicities should be discussed with the protocol team via email.

Subjects who develop a Grade 4 adverse event or toxicity judged to be **MVC related** will have the study drug permanently discontinued. Exemptions include: asymptomatic elevations of CPK, cholesterol or triglycerides. For these laboratories, medication may be continued at the discretion of the site investigator and laboratories repeated within 2 weeks. For other Grade 4 events, if the toxicity or laboratory elevation is thought not to be due to MVC, MVC may be continued and laboratories repeated within 2 weeks. If it is not possible for the investigator to discern the causative agent or MVC is possible/ probably the causative agent, then all MVC must be discontinued. A new regimen may be chosen at the discretion of the local investigator. Subjects experiencing Grade 4 adverse events requiring permanent discontinuation of MVC therapy should be followed weekly until resolution of the adverse event. Once Grade 4 is resolved the subject should be removed from study.

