6.2.2 On-Study Evaluations

Evaluations during the MVC treatment intensification period will occur on weeks 2, 4, 8, 12, and 24. An addition visit will occur after MVC treatment intensification on week 36. Study visits at week 2 and 4 will have a visit window period of 1 week. For study visits at week 8, 12, 24 and 36 there will be a 2 week visit window period. In instances of virologic failure and/or premature treatment discontinuation evaluations would also need to occur as soon as possible.

Total blood volume for laboratory evaluations during MVC treatment intensification (week 2 to week 24) will be approximately 200 mL.

Lumbar puncture – 25 mL cerebral spinal fluid (week 4 and 24)

Total blood volume for laboratory evaluations during post-MVC treatment intensification (week 36) will be approximately 40 mL.

6.2.3 Evaluations and plan for registered subjects that do not complete week 4 of the study:

- a. Those subjects that do not start treatment will be replaced and will have no follow-up evaluations performed.
- b. Subjects that discontinue antiretroviral therapy and/or MVC before week 4 will be replaced and will have no follow-up evaluations performed.

6.2.4 Evaluations and plan for randomized or registered subjects that complete week 4 but not the remainder of the study:

- a. Subjects who complete week 4 of the study but then discontinue their antiretroviral regimen and/or MVC will not be replaced and will not be discontinued from the study.

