7.2.4 Rash

Grade 1 or 2

MVC may be continued without interruption. Subjects with a Grade 1 or 2 rash may be treated symptomatically with permitted antipyretic, antihistamine, and/or non-steroidal anti-inflammatory medications, but should be monitored closely by the local investigator.

Grade 3 or 4

A rash of Grade 3 or 4 necessitates that all MVC should be held for any Grade 3 or 4 rash unless the rash is determined to be unrelated to MVC. Upon resolution to Grade ≤ 1 , the subject should be removed from study.

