7.2.5 Nausea and Vomiting

Grade 1 or 2

MVC may be continued without interruption. Subjects with Grade 1 and 2 nausea or vomiting may be treated symptomatically with permitted oral antiemetic therapies or antiemetic suppositories. Subjects should be instructed to take medications with food.

Grade 3 or 4

Subjects with Grade 3 or 4 MVC-related nausea and vomiting should interrupt MVC until the toxicity grade returns to Grade ≤ 2 or to baseline and be treated symptomatically. If Grade ≥ 3 nausea and vomiting recurs upon the resumption of MVC despite symptomatic treatment, MVC should again be interrupted and the protocol team notified for possible study discontinuation.

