7.2.11 CK Elevations

Asymptomatic elevations in CK or elevations due to exercise **should be repeated (within 2-4 weeks) to assure that they are transient or due to exercise and** will not require a change in study treatment. Elevations in CK $> 20 \times$ ULN should be repeated after the subject has abstained from exercise for ≥ 24 hours. For persistent CK elevations $>20 \times$ ULN should prompt a permanent discontinuation of MVC and subjects should be discontinued from study and the protocol team should be notified.

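### Section 7 removes subjects who stop MVC for listed toxicities at any time, section 6.2.4a keeps them on study after week 4, and nothing says which rule prevails

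*Combined protocol and SAP*

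**What the plan says.** All references are to the combined protocol and SAP.

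**Retention.** Section 6.2.4a covers subjects who complete week 4 and then stop their antiretroviral regimen or MVC. Such a subject "will not be replaced and will not be discontinued from the study". Earlier stops are handled differently in 6.2.3b: "Subjects that discontinue antiretroviral therapy and/or MVC before week 4 will be replaced and will have no follow-up evaluations performed".

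**Removal.** Five paragraphs of section 7 order it:
- 7.1.1, Grade 1 or 2 events that end MVC: "Those subjects experiencing Grades 1 or 2 adverse events which results in discontinuation of the MVC should be removed from the study".
- 7.1.2, symptomatic Grade 3 events considered MVC-related, after weekly follow-up: "Once Grade 3 is resolved the subject should be removed from study".
- 7.2.3 (printed under 7.1), Grade 4 events requiring permanent discontinuation of MVC, after weekly follow-up: "Once Grade 4 is resolved the subject should be removed from study".
- 7.2.4, Grade 3 or 4 rash not judged unrelated to MVC: on resolution to Grade 1 or less, "the subject should be removed from study".
- 7.2.11, persistent CK above 20 times ULN: this "should prompt a permanent discontinuation of MVC and subjects should be discontinued from study".

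**Discretion.** Sections 7.2.5, 7.2.6, 7.2.8 and 7.2.10 go less far. After a recurrence, in the words of 7.2.5, "MVC should again be interrupted and the protocol team notified for possible study discontinuation". Section 7.2.9 stops MVC for low creatinine clearance and orders no removal.

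**Related rules.** Section 8.1 lists MVC toxicity as a reason to stop treatment. Section 8.2 lists reasons to leave the study and names toxicity only for failure to complete week 4. Section 6.2.7 keeps virologic failures on study after MVC is stopped. Section 6.2.8 gives the week 36 visit to those who complete 24 weeks of MVC and is silent on early stoppers.

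**The concern.** A site whose subject stops MVC at week 10 because of a Grade 2 event cannot obey both 6.2.4a and 7.1.1. Sites may resolve this differently.

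The subjects concerned are those who did not tolerate the drug, and safety and tolerability is objective 1.2.4. If section 7 prevails, their follow-up is cut short for a reason tied to the outcome being measured. After week 4 the schedule in section 6.1 has plasma RNA only at weeks 24 and 36, so removal before week 24 takes away the one remaining scheduled RNA during the 24-week period. It also takes away the week 24 CD4 and safety laboratory tests. Section 9.4.3.1 item 9 compares toxicity proportions between time points with McNemar's test, which needs pairs; a removed subject has no later member of the pair.

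**Working it through.** **1. Do the rules overlap?** Before week 4 they do not: 6.2.3b ends follow-up and replaces the subject, which is compatible with removal. From week 4 to week 24, a period of 20 weeks, 6.2.4a retains the subject and the five section 7 paragraphs remove the same subject. Those paragraphs carry no timing condition.

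**2. Is there a ranking?** None is stated. Section 8.1 points to section 7, but as grounds for stopping treatment. Sections 8.2 and 6.2.7 fit retention.

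**3. When does removal take effect?** Under 7.1.1 and 7.2.11 no resolution period is given, so it is immediate. Under 7.1.2, 7.2.3 and 7.2.4 it comes after resolution, so scheduled visits before then still take place.

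**4. What is lost and what remains?** Lost: scheduled visits after removal, including week 24. Kept: the premature-discontinuation visit in 6.1 (CD4, RNA, hematology, chemistry); weekly follow-up to resolution under 7.1.2 and 7.2.3; and, under 6.4, additional safety monitoring with SAE reporting for 8 weeks, then four event types.

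**5. How many subjects?** The protocol states no expected toxicity discontinuation rate for this trial, so there is no figure to reproduce. Inputs:
- N = 30 (3.1), taken as all on MVC at week 4.
- Adverse-event discontinuation p = 4.2% in treatment-naïve patients (2.3), from a 48-week study (2.2.1.2, Impact on CD4 Recovery; reference 25 also has 48 weeks in its title).
- p = 4.9% on twice-daily MVC in treatment-experienced patients (2.1.1.1). The text describes 48 weeks of treatment, but the title of the cited report, reference 22, says 24-week results.

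With constant hazard over T weeks, the chance of a stop in the 20 weeks is q = 1 − (1 − p)^(20/T). The expected number is 30q, and the chance of at least one is 1 − (1 − q)^30.

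| p | T (weeks) | q | Expected of 30 | Chance of at least one |
|---|---|---|---|---|
| 0.042 | 48 | 0.0177 | 0.53 | 41.5% |
| 0.049 | 48 | 0.0207 | 0.62 | 46.6% |
| 0.049 | 24 | 0.0410 | 1.23 | 71.5% |

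Simple proportional scaling, 30 × p × 20/T, gives 0.53, 0.61 and 1.23.

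**The case against.** **Specific over general.** Section 7 could be read as the specific rule that overrides the general 6.2.4a. That reading is possible, but the protocol does not state it, and 8.1, 8.2 and 6.2.7 lean the other way.

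**Nine conflicting paragraphs.** A reader might add the four paragraphs that mention possible study discontinuation. They do not contradict 6.2.4a. They refer the case to the protocol team after a recurrence, and 8.2 already allows discretionary and life-threatening exits with no week-4 limit. This part of the objection stands, so the point is confined to five paragraphs.

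**Week 36.** A reader might also blame section 7 for the loss of week 36. But 6.2.8 leaves that visit unassigned for early stoppers even if 6.2.4a prevails, and week 36 is in no endpoint in 9.2 and no analysis in 9.4. It is a separate gap, best closed in the same amendment.

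**Little analysis depends on the data.** This largely stands. An off-drug week 24 CD4 says nothing about the slope on MVC. Item 9 describes toxicity during intensification and does not say which time points it pairs or how off-drug subjects count. What remains is the paired toxicity comparison and the RNA and safety follow-up of subjects who stopped for toxicity.

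**The size leans high.** A figure of about one subject is tempting, but the protocol text supports 0.53 to 0.62. The 1.23 rests on a reference title alone, and a 24-week base for the 4.2% has no support.

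**Conclusion.** Wrong as written, minor severity. The conflict between 6.2.4a and 7.1.1, 7.1.2, 7.2.3, 7.2.4 and 7.2.11 is plain in the text and unresolved.

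On the 48-week basis it is slightly more likely than not that no subject is affected (53% to 58%). On the 24-week reading of the 4.9% the chance of none is about 28%. The counts rest on rates from other populations, constant hazard, and the inclusion of every adverse-event stop. Clustering of stops before week 4, or stops under paragraphs without a removal order, would lower them.

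A reader might infer damage to the gene-expression endpoint. The documents do not support that: once MVC is stopped there is no on-MVC week 24 sample under either rule.

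**What to change.** - In 7.1.1, 7.1.2, 7.2.3, 7.2.4 and 7.2.11, replace removal from the study with: *discontinue MVC and, if past week 4, follow per 6.2.4*. Keep the weekly follow-up to resolution where it is given.
- Keep the exits in 8.2, and leave 7.2.5, 7.2.6, 7.2.8 and 7.2.10 to the team's discretion.
- Extend 6.2.8 so that subjects who stop MVC after week 4 also have the week 36 visit.
- In 9.4.3.1 item 1, flag CD4 values taken after MVC is stopped as off-drug and keep them out of the MVC-period slope. The model has only pre-MVC and MVC periods, so a retained subject's week 24 value could otherwise be coded as MVC.

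The cost is a wording amendment to five paragraphs and 6.2.8, one added analysis sentence, and a few visits of the existing schedule for, in expectation, 0.5 to 1.2 subjects. MVC is stopped exactly as section 7 now requires. The gain is complete off-drug safety, RNA and CD4 follow-up for those subjects; no on-MVC expression sample is recovered.

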7.2.8 AST/ALT Elevations

Grade 1 or 2

MVC may be continued.

Grade 3

All grade 3 or 4 elevations of AST/ALT should be discussed immediately with the protocol team via email. MVC may be continued for Grade 3 AST/ALT elevations at the discretion of the site investigator after discussion with the protocol team. Careful assessments should be done to rule out the use of alcohol, non-study medication-related drug toxicity, or viral hepatitis as the cause of the Grade 3 elevation. The possibility of lactic acidosis syndrome should also be explored.

Grade 4

MVC should be held for AST or ALT Grade 4 elevations until the toxicity returns to Grade ≤ 2 . If the Grade 4 elevation in AST or ALT recurs, MVC should again be interrupted and the protocol team notified for possible study discontinuation.

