9.5 Monitoring

The safety and tolerability of the study medications will be monitored by means of adverse event reports (AER) and monthly toxicity reports that will include laboratory and clinical data. These reports will be discussed by the protocol team on monthly conference calls.

Data and Safety Monitoring Board, it is the responsibility of the Principal Investigator and the CCTG protocol team to interpret the toxicity data and make any decisions needed to protect patients from undue risk. Accrual and toxicity summaries will be provided to the Protocol Chairs and CCTG Investigators by the Data Manager and Biostatistician.

If more than **five** patients develop virologic failure or discontinue MVC due to an adverse event or laboratory toxicity, an independent interim review committee will be established to review the study results to date. The interim review committee will be composed of at least 3 people (including one statistician) outside the protocol team. The committee will make specific recommendations about changes to the study protocol.

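### Section 7 gives opposite stopping instructions for MVC-related Grade 4 nausea and vomiting, and for Grade 4 diarrhea and AST/ALT elevations when MVC is or may be the cause, and does not say which prevails

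*Combined protocol and SAP*

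**What the plan says.** **General rule (7.2.3, Grade 4).** Subjects whose Grade 4 event is judged MVC-related "will have the study drug permanently discontinued. Exemptions include: asymptomatic elevations of CPK, cholesterol or triglycerides". Beyond those exemptions, staying on drug depends on attribution: "For other Grade 4 events, if the toxicity or laboratory elevation is thought not to be due to MVC, MVC may be continued". If the investigator cannot tell the cause, or "MVC is possible/ probably the causative agent, then all MVC must be discontinued". After follow-up of a permanent discontinuation, "Once Grade 4 is resolved the subject should be removed from study".

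**Event-specific rules.**
- 7.2.5: "Subjects with Grade 3 or 4 MVC-related nausea and vomiting should interrupt MVC until the toxicity grade returns to Grade" 2 or lower, or to baseline. It then covers recurrence once MVC has been resumed.
- 7.2.6: Grade 3 or 4 diarrhea that does not respond to antimotility agents, with no other cause established, leads to interruption until improvement. It also provides for recurrence on resumption.
- 7.2.8: "MVC should be held for AST or ALT Grade 4 elevations until the toxicity returns to Grade" 2 or lower. On recurrence MVC is interrupted a second time, so it must have been restarted.

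**Precedence.** The sentence "Please refer to the subsequent sections for management of specific events" stands in 7.1.2 (Grade 3). The Grade 4 paragraph has no counterpart. Section 8.1 lists MVC toxicity as a reason to stop treatment and refers back to section 7.

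**Use of the count.** Under 9.5 an independent review committee is set up if more than five patients have virologic failure or "discontinue MVC due to an adverse event or laboratory toxicity".

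**The concern.** An investigator with a patient vomiting at Grade 4 because of MVC finds one section that ends treatment and study participation, and another that interrupts MVC and foresees its return. Both are written as instructions. This is a safety matter first, since section 2.1.1.1 lists hepatotoxicity among the label warnings and AST/ALT is one of the three affected events.

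It is also a counting matter. The only numerical safety threshold in the plan, in 9.5, counts patients who discontinue MVC for toxicity. A patient managed under 7.2.3 is counted. A patient with the same event managed under 7.2.5, 7.2.6 or 7.2.8 is held and restarted, and 9.5 does not say whether that counts.

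**Working it through.** **Step 1: set the rules side by side for a Grade 4 event.**

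| Event | Under 7.2.3 | Under the specific section | Overlap |
|---|---|---|---|
| Nausea/vomiting, MVC-related | Permanent stop, then off study | 7.2.5: interrupt, resumption foreseen | Full: same grade, same attribution |
| Diarrhea, no other cause established | Permanent stop if judged MVC-related; discontinue if MVC is possible or cause unclear | 7.2.6: interrupt, resumption foreseen | Where MVC is the cause or cannot be excluded |
| AST/ALT, any attribution | As for diarrhea; may continue if thought unrelated | 7.2.8: hold, resumption implied | Where MVC is the cause or cannot be excluded |

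None of the three is among the exemptions that 7.2.3 names (asymptomatic CPK, cholesterol and triglycerides). Nausea and vomiting is the cleanest case, because 7.2.5 is itself limited to MVC-related events and so needs no inference about attribution. For a merely possible cause, 7.2.3 says MVC must be discontinued without repeating the word permanently. I read it as a stop because section 7 uses hold and interrupt for temporary measures.

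Two events lie outside the conflict. Grade 3 or 4 rash (7.2.4) is held and the subject then leaves the study, with no resumption. The anemia and neutropenia rule (7.2.10) concerns events attributed to NRTIs.

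**Step 2: look for a tie-breaker.** The 7.1.2 pointer covers Grade 3 only, and 8.1 refers back to section 7. Neither settles Grade 4.

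**Step 3: effect on the 9.5 trigger.** The plan gives no operating figure for the trigger, so there is none to reproduce. Inputs:
- n = 30 (section 3.1).
- Threshold: more than five, so 6 or more (9.5).
- Base rate: 4.9%, the adverse-event discontinuation rate on twice-daily MVC in section 2.1.1.1. It comes from a different population and leaves out virologic failure, which also counts, so it serves only to set a scale. A 10% base is assumed as an alternative.
- q: the share of patients with a disputed Grade 4 event who are not otherwise counted. The documents give no value; 2, 5 and 10 points are assumptions.

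P(X ≥ 6) = 1 − Σ (k = 0 to 5) C(30, k) p^k (1 − p)^(30 − k), with p = base if disputed events do not count and p = base + q if they do.

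| Base | q = 0 | q = 2 points | q = 5 points | q = 10 points |
|---|---|---|---|---|
| 4.9% | 0.003 | 0.015 | 0.070 | 0.284 |
| 10% (assumed) | 0.073 | 0.143 | 0.289 | 0.573 |

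Expected disputed cases are 30 × q = 0.6, 1.5 and 3.0.

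**Step 4: effect on the sample.** Section 9.4.1 plans 30 week-24 arrays. A patient removed before week 24 under 7.2.3 could cost one of them; a patient held and restarted could still contribute. This loss is itself uncertain, because 6.2.4 keeps on study those who stop MVC after completing week 4.

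**The case against.** **A specific rule normally overrides a general one.** The event sections carry explicit Grade 3 or 4, or Grade 4, headings, and this may well be what was meant. But the protocol says so only under Grade 3, while the Grade 4 paragraph has mandatory wording and exemptions of its own. The reading is available, not stated.

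**The protocol team sees these cases.** Section 7.2.3 asks for Grade 4 toxicities to be discussed with the team by email, 7.2.8 asks for immediate discussion of Grade 3 or 4 AST/ALT elevations, and 9.5 provides monthly toxicity review. This stands, and it makes opposite handling at two sites less likely. It does not give the team one written rule to apply.

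**The trigger has a plain reading.** Since section 7 separates holding from discontinuing, a patient who restarts has not discontinued. That is reasonable, but it does not settle which rule applies to the patient in the first place, and 9.5 could say it in one sentence.

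**Stronger readings that the documents do not support.**
- A reader might infer that the tolerability endpoint also shifts. It does not: objective 1.2.4, endpoint 3 in 9.2.2 and item 9 in 9.4.3.1 use graded events, so a Grade 4 ALT counts the same whether MVC is held or stopped.
- A reader might take the 7.2.3 exemptions as exhaustive. The wording is that exemptions include those named, which is formally open, although the next sentences send other Grade 4 events to the attribution rule.
- A reader might conclude that the plan has no stopping rule. It has two that conflict, for three event types.
- A reader might size the problem from the liver rates in 2.1.1.1. Those pool Grades 3 and 4, disregard baseline values and are not limited to MVC-related events. AST above 5 × ULN was 4.5% on MVC against 2.9% on placebo; ALT was 2.4% against 3.4%. They give no rate for MVC-related Grade 4 events.

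**Conclusion.** The point holds and the text is wrong as written. The contradiction is direct for MVC-related Grade 4 nausea and vomiting. It is conditional for Grade 4 diarrhea and AST/ALT elevations, where it arises when MVC is the cause or cannot be excluded.

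The numerical consequence is confined to the 9.5 trigger: 0 or 1 per affected patient towards the six needed. At the 4.9% base and an assumed 2% of patients with disputed events, the trigger probability stays small (0.015). It becomes material only if such events are more common, and the documents give no basis for choosing a rate. The case for amending therefore rests on the conflicting safety instructions and the unclear count, not on a predicted number of cases. No endpoint definition, power figure or error rate depends on it.

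**What to change.** 1. Reconcile 7.2.3 with 7.2.5, 7.2.6 and 7.2.8, and state for each event which section prevails at Grade 4. Which clinical rule applies is for the investigators to decide.
2. State in 9.5 whether a hold followed by resumption counts as discontinuing MVC for the more-than-five trigger.
3. In the same pass, align the removal from study in 7.2.3 with 6.2.4, so that it is clear whether these patients still attend week 24.

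The cost is a short wording amendment, best made before enrolment. Sample size, visit schedule and analysis methods are unchanged, and 9.4.3.1 item 9 needs no edit.
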